Study Protocol

Randomized Evaluation of Heart Failure with Preserved Ejection Fraction (HFpEF) Patients with Acute Heart Failure and Dopamine (ROPA-OP) Trial

clinicaltrials.gov Identifier: NCT01901809

Protocol Date: August 8, 2013

Principal Investigator:

[name]

The Johns Hopkins University School of Medicine.

[name]

[name]

[contact] [contact]

JHM IRB - eForm A – Study Protocol

- Use the section headings to write the JHM IRB eForm A, inserting the appropriate material in each. If a section is not applicable, leave heading in and insert N/A.
- When submitting JHM IRB eForm A (new or revised), enter the date submitted to the field at the top of JHM IRB eForm A.

1. Abstract

- a. Provide no more than a one page research abstract briefly stating the problem, the research hypothesis, and the importance of the research.

Heart Failure with preserved Ejection Fraction (HFPEF) accounts for 40-50% of all heart failure patients with a frequency of hospital admissions for acute decompensation and short and long term mortality similar to patients with heart failure with reduced ejection fraction (HFREF). Patients with HFPEF are often preload dependent and despite admission to the hospital for acute decompensated heart failure (ADHF), are typically difficult to diurese due to the development of acute kidney injury. In contrast to the many randomized trials showing mortality and morbidity benefit of ACE inhibitors and beta blockers in patients with heart failure with reduced ejection fraction, no drugs have shown a benefit in patients with HFPEF. Furthermore, patients hospitalized for ADHF who develop acute kidney injury during their hospital stay have longer hospitalizations, more frequent re-hospitalizations for heart failure, and worse short term survival compared to those without acute kidney injury. We hypothesize that changing the method of diuresis and/or the addition of low-dose dopamine for the treatment of ADHF in patients with HFPEF will reduce renal injury, resulting in a shorter length of stay, and decrease hospital readmissions over the ensuing year.

2. Objectives (include all primary and secondary objectives)

To evaluate the effects of low dose dopamine and diuretic strategy (intermittent versus continuous) on renal function in patients with HFPEF admitted with acute heart failure.

Primary end point:

1. Percent change in creatinine from randomization to 72 hrs from treatment protocol initiation.

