Secondary end points:

1. Change in incidence of acute kidney injury (AKI) as defined by Kidney Disease: Improving Global Outcomes (KDIGO criteria summarized below) from randomization to 72 hrs.¹

2. Incidence of AKI as determined by urine output at 72 hrs (KDIGO criteria, summarized below).¹
3. Change in creatinine at 72 hrs adjusted for volume of fluid removal
4. Change in serum cystatin C randomization to 72 hrs
5. Change in NT pro-BNP from randomization to 72 hrs
6. Volume of diuresis measured in liters
 - a) Cumulative volume of diuresis measured in liters
 - b) Cumulative volume of diuresis measured in liters adjusted for BSA
7. Net weight loss at 72 hrs in kg
8. Need for increase in intravenous diuretic dose
9. Change in distance during 6 minute walk test
 - a) From admission to 72 hrs
 - b) From admission to discharge
10. Global well-being assessment score from admission to 72 hrs, and at discharge. To be assessed by a Visual Analog Scale (VAS).
11. Subjective dyspnea score from admission to 72 hrs, and at discharge. To be assessed by a Visual Analog Scale (VAS).
12. Change in frailty index from admission to 72 hrs, and at discharge. To be assessed by the Johns Hopkins Older Americans Independence Center Online Frailty Assessment Tool
13. Length of stay of hospitalization in days
14. 30 day, 6 month, and 1 year hospital readmission or ER visit for major adverse cardiovascular event, heart failure, renal failure (development of CKD, ESRD, or dialysis need by KDIGO criteria), syncope, or arrhythmia. Readmission events will be adjudicated by a Clinical Event Committee consisting of 2-3 cardiologists not directly in contact with patients enrolled in the study.

KDIGO AKI Definition¹:

AKI is defined by any of the following 3 criteria:

1. Increase in serum creatinine by ≥ 0.3 mg/dl (≥ 26.5 $\mu\text{mol/l}$) within 48 hours; OR
2. Increase in serum creatinine to ≥ 1.5 times baseline, which is known or presumed to have occurred within prior 7 days; OR
3. Urine volume < 0.5 ml/kg/h for 6 hours

Stages of AKI as defined by KDIGO Criteria are as follows:

Stage	Serum Creatinine	Urine Output
1	1.5-1.9 times baseline OR ≥ 0.3 mg/dl (≥ 26.5 $\mu\text{mol/l}$) increase	< 0.5 ml/kg/h for 6-12 hours

2	2.0-2.9 times baseline	<0.5 ml/kg/h for \geq 12 hours

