 - a. Intermittent furosemide diuretic therapy from above (1.) with the addition of dopamine at 3 µg/kg/min
4. Continuous infusion furosemide diuretic therapy plus infusion of low dose intravenous dopamine (3 µg/kg/min)
 - a. Continuous furosemide diuretic therapy from above (2.) with the addition of dopamine at 3 µg/kg/min

Conversion guidelines:

2 mg oral furosemide = 1 mg intravenous furosemide

1 mg torsemide = 2 mg furosemide

1 mg bumetanide = 40 mg furosemide

Diuretic titration guidelines:

Should the patient fail to demonstrate adequate diuresis (net negative urine output of at least 500ml in 12 hrs) in response to the first treatment dose, the subsequent diuretic dose to be administered 12 hrs later (dose #2) will be doubled, or the continuous infusion will be doubled, with the goal of net negative urine output of 1 liter over 24 hrs. This titration plan can continue until adequate diuresis is achieved (at least net negative 1L urine output over 24 hr period).

Maximum Diuretic Dose:

The maximum dose permitted within study protocol will be furosemide 200 IV twice daily, or a total dose of furosemide 400 IV over 24 hrs. Should the primary team feel the patient needs higher dosing or the addition of a thiazide diuretic (or alternative agent), the patient will be considered treatment failure and will be removed from the study.

Electrolyte Repletion Guidelines:

The primary team will obtain basic metabolic panels on all study participants every 12 hours for the duration of the study. It will be the responsibility of the primary team to replete electrolytes with the goals of potassium > 4.0, and magnesium >2.0 as needed for study participants.

Fluid and Salt Restrictions:

Each study participant will be maintained on a daily 2 liter fluid and 2 gm sodium restricted diet, to be ordered by the primary team.

Treatment beyond trial end-point guidelines:

Intravenous diuretic therapy with or without dopamine according to the protocol will be continued until the treating physician decides the patient no longer requires intravenous diuretic therapy or 72 hours, whichever comes first.

All other heart failure or non-heart failure treatments will be left to the discretion of the primary team from the time of the patient's admission to the hospital and/or enrollment in the study. This includes anti-hypertensives, anti-arrhythmic drugs, and any other therapies deemed necessary for the treatment of the study subject.

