After 72 hrs, the study drug will be discontinued, a primary assessment will be made of primary and secondary endpoints, and all further treatment is at the treating physician's discretion.

Note: Study participants will be permitted to cross over into non-assigned arms of the study, however the study analysis will be completed as an intention-to-treat study. It will be left to the discretion of the primary team, with supervision from the study investigators as to whether a cross over is necessary within the 72 hr study time frame.

Baseline Assessments and Data to be Recorded (all are standard of care unless indicated by *)

1. Directed history and physical exam, focused on signs and symptoms of congestion/volume overload
2. Vital signs (HR, BP, O2 saturation, weight, height)
3. Home medications
4. Basic metabolic panel including serum creatinine, BUN, electrolytes and magnesium
5. Serum Pro-BNP level
6. Serum Cystatin C*
7. High-sensitivity troponin
8. Baseline electrocardiogram
9. Transthoracic echocardiogram if one has not been obtained within 1 year prior to admission
 - i. Including left ventricular (LV) ejection fraction, LV dimensions, left atrium size (LA), LV mass, right ventricular function parameters (RVSP), valvular assessment
10. 6 min walk test*
11. Patient Global Well being assessment by VAS*
12. Dyspnea assessment by VAS*
13. Frailty Index*
14. Blood sample for biomarkers and genetic testing for heart failure*
15. Urine sample for biomarkers*

24 hr Assessment:

1. Routine vitals assessment with weight recording
2. I/O assessment – to be recorded and totaled for each 12 period
3. Twice daily basic metabolic panel and serum magnesium

72 hr Assessment and Data to be Recorded:

1. Routine vitals assessment with weight recording
2. I/O assessment – to be recorded and totaled for each 24 period
3. Twice daily basic metabolic panel and serum magnesium
4. Serum Pro-BNP level*
5. Serum Cystatin C*
6. High-sensitivity troponin
7. 6 min walk test*
8. Patient Global Well being assessment by VAS*
9. Dyspnea assessment by VAS*
10. Frailty Index*
11. Changes in cardiovascular medications
12. Assessment for serious cardiovascular events

At Discharge Assessment and Data to be recorded:

1. Routine vitals assessment with discharge weight recording
2. I/O assessment – to be recorded and totaled for each 24 period
3. Basic metabolic panel including creatinine, BUN
4. Serum Pro-BNP level
5. Serum Cystatin C*
6. High-sensitivity troponin
7. 6 min walk test*

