14. 30 day, 6 month, and 1 year hospital readmission or ER visit for major adverse cardiovascular event, heart failure, renal failure (development of CKD, ESRD, or dialysis need by KDIGO criteria), syncope, or arrhythmia. Readmission events will be adjudicated by a Clinical Event Committee consisting of 2-3 cardiologists not directly in contact with patients enrolled in the study.

KDIGO AKI Definition¹:

AKI is defined by any of the following 3 criteria:

1. Increase in serum creatinine by ≥ 0.3 mg/dl (≥ 26.5 $\mu\text{mol/l}$) within 48 hours; OR
2. Increase in serum creatinine to ≥ 1.5 times baseline, which is known or presumed to have occurred within prior 7 days; OR
3. Urine volume < 0.5 ml/kg/h for 6 hours

Stages of AKI as defined by KDIGO Criteria are as follows:

Stage	Serum Creatinine	Urine Output
1	1.5-1.9 times baseline OR ≥ 0.3 mg/dl (≥ 26.5 $\mu\text{mol/l}$) increase	< 0.5 ml/kg/h for 6-12 hours
2	2.0-2.9 times baseline	< 0.5 ml/kg/h for ≥ 12 hours
3	3.0 times baseline OR increase in serum creatinine to ≥ 4.0 mg/dl (≥ 353.6 $\mu\text{mol/l}$) OR initiation of renal replacement therapy OR, in patients < 18 years, decrease in eGFR to < 35 ml/min per 1.73 m ²	< 0.3 ml/kg/h for ≥ 24 hours OR Anuria for ≥ 12 hours

a. Statistical plan including sample size justification and interim data analysis.

1. Overview:

- a. This is a factorial design study evaluating two simultaneous unrelated interventions. Sample size justification and primary endpoint analysis is described below.

2. Analysis of Primary Endpoints:

- a. The primary analysis will be conducted on an intention-to-treat basis. Non-parametric testing for the continuous primary endpoint (creatinine) will be performed using the Wilcoxon-Mann-Whitney U test. Confirmatory test for interaction between dopamine and diuretic strategy will be performed with linear regression analysis with dopamine*diuretic term, $p=0.10$ for significance.

3. Sample Size Justification:

- a. A difference of 30% in creatinine pre and post- treatment is considered to be clinically meaningful. Setting parameters as follows: two-sided, alpha (Type I error rate) of 0.05, power of 0.80, and using mean creatinine calculations based on our own retrospective experience at

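### AKI by urine output is defined over 6 hours, but the plan lists only 12- and 24-hour intake/output totals and no rule for deriving the endpoint; a normal total cannot exclude a qualifying 6-hour episode

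*Combined protocol and SAP*

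**What the plan says.** **The endpoints.** Secondary endpoint 2 (section 2, repeated in section 7.b) is "Incidence of AKI as determined by urine output at 72 hrs (KDIGO criteria, summarized below"). Secondary endpoint 1 is "Change in incidence of acute kidney injury (AKI) as defined by Kidney Disease: Improving Global Outcomes". Under the KDIGO definition in both sections, "AKI is defined by any of the following 3 criteria", and the third is "Urine volume < 0.5 ml/kg/h for 6 hours". The urine criterion therefore enters both endpoints.

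**The data.** Section 4.a lists intake/output at the 24 hr Assessment as "to be recorded and totaled for each 12 period". At the 72 hr and discharge assessments it is "to be recorded and totaled for each 24 period". The unit is not printed; hours is the natural reading. No section asks for urine volumes over 6 hours or less. A urinary catheter is encouraged, partly so that intake/output is more accurate, but it is optional (section 4.a, Foley Catheter Placement).

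**The analysis.** Section 7, Analysis of Secondary Endpoints, gives summary statistics and a significance level. It contains no derivation rule for AKI by urine output.

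**The concern.** The criterion works on a 6-hour scale and the listed data on 12- and 24-hour scales. A total fixes the average over its period but not the distribution within it, so an oliguric stretch can be offset by brisk diuresis before or after. That pattern is plausible in patients receiving intravenous furosemide.

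If the case report form holds only the listed totals, endpoint 2 and the urine part of endpoint 1 would be classified by a coarser rule than the one defined. If finer chart entries are used instead, the choice of window and weight and the treatment of gaps are left open until the data are in hand, in a trial whose treatment is not blinded.

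**Working it through.** The plan states no figure on this point, so there is none to reproduce. The check is whether the listed totals determine the 6-hour criterion.

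**Inputs.** Threshold 0.5 ml/kg/h for 6 hours (sections 2 and 7); totals per 12 and per 24 hours (section 4.a); 140 patients (section 7, Sample Size Justification); the titration guideline's adequate response, "net negative urine output of at least 500ml in 12 hrs" (section 4.a). Assumed: complete collection, the criterion read as a mean rate over the window, and 80 kg where a weight is needed, because the documents give no mean weight.

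**1. Threshold volumes.** 0.5 × 6 = 3 ml/kg per 6 h; 0.5 × 12 = 6 ml/kg per 12 h; 0.5 × 24 = 12 ml/kg per 24 h.

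**2. A low total implies a qualifying window.** If both 6-hour halves of a 12-hour period reach 3 ml/kg, the total reaches 6. If all four quarters of a 24-hour period reach 3 ml/kg, the total reaches 12. A total below 6 or 12 ml/kg therefore forces at least one 6-hour block below 3 ml/kg.

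**3. A normal total does not exclude one.** Let one 6-hour window run at rate r.
- 12-hour total: hidden if the other 6 h average at least (6 − 6r)/6 = 1.0 − r.
- 24-hour total: hidden if the other 18 h average at least (12 − 6r)/18.

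| Rate r in the 6-hour window | Other 6 h (12-h total) | Other 18 h (24-h total) |
|---|---|---|
| 0 ml/kg/h | 1.0 ml/kg/h | 12/18 = 0.67 ml/kg/h |
| 0.3 ml/kg/h | 0.70 ml/kg/h | 10.2/18 = 0.57 ml/kg/h |

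These limits do not depend on body weight.

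**4. Against the plan's own figure.** With no other losses, an adequate 12-hour response means urine = 500 ml + intake. This clears 6 ml/kg whenever weight ≤ (500 + intake)/6: 83 kg with no intake, 167 kg with 500 ml intake, whatever the 6-hour pattern. At 80 kg with no intake, 500 ml passed entirely in the first 6 hours gives 500/(80 × 12) = 0.52 ml/kg/h over 12 hours, with no urine in the next 6.

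**5. When the assumptions fail.**
- Incomplete collection: at a true 0.6 ml/kg/h, a 12-hour total reads low once more than 7.2 − 6 = 1.2 ml/kg is uncollected (96 ml at 80 kg). For a 24-hour total the figure is 14.4 − 12 = 2.4 ml/kg (192 ml).
- Hour-by-hour reading: a repeating pattern of five hours at 0.3 and one at 1.2 ml/kg/h averages (5 × 0.3 + 1.2)/6 = 0.45, or 5.4 ml/kg over 12 h. The total is low although no run of six hours is low throughout.

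Either failure can produce false positives, so the net direction of error is not fixed.

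**The case against.** The strongest reply is that an interval for totalling is not an interval for measuring. Intake/output is not marked as an investigational item and is charted by nursing staff, so entries every few hours may well exist. If so, only a derivation sentence is missing. This stands. A reader might infer that urine is measured only every 12 or 24 hours and that the endpoint is unmeasurable; the documents do not say that. What remains is that no section states a finer interval or says that finer entries feed the endpoint.

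Second, fixed 6-hour windows do not fully cure the problem. Six hours without urine split 3 + 3 across two windows are hidden if the other 3 hours of each average at least 3/3 = 1.0 ml/kg/h. This also stands: fixed windows are an improvement, and rolling windows are better where the entries allow.

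Third, no impact is shown. The zero-intake example is artificial when the plan allows 2 litres of fluid a day. This is correct as to frequency, but greater intake raises the total and so does not remove the possibility of a hidden episode.

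Fourth, this is one of 14 secondary endpoints. That is agreed and limits the weight of the point. The choice of weight and the start of the 72 hours are side clarifications with no shown effect.

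**Conclusion.** The point holds conditionally. Deriving the urine criterion from the data items as listed would miss 6-hour episodes offset by higher output in the rest of the period. For a window without urine the offset needed is 1.0 ml/kg/h over the other 6 hours, or 0.67 ml/kg/h over the other 18. This rests on three conditions that the plan does not state: derivation from the totals, complete collection, and a mean-rate reading.

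Stronger readings are not supported:
- **That the trial will under-count AKI.** Uncollected voids can make totals falsely low, so neither the number of missed events nor the net bias can be determined.
- **That the bolus and infusion arms would be misclassified differently.** This would need more uneven flow under boluses, on which the documents give no data.
- **That the main result is at risk.** The primary endpoint and creatinine-based AKI do not use urine volume.

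The plan should be changed, but the consequence is confined to endpoint 2 and the urine part of endpoint 1. Separately, the Stage II and III AKI rules in section 4.f and under Early stopping rules in section 7 rely on stages that include urine criteria, and the data used to judge them are not stated. A 24-hour total of 12 ml/kg can contain 12 hours without urine if the other 12 average 1.0 ml/kg/h. Those passages and the recording intervals must be reconciled.

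**What to change.** **Change.** Reword the section 4.a intake/output item so that urine volumes are extracted from the nursing records in intervals of at most 6 hours up to 72 hours. In section 7, derive endpoint 2 and the urine part of endpoint 1 from these volumes:
- read the criterion as a mean rate over 6 hours;
- use rolling 6-hour windows where entries are fine enough, and otherwise fixed windows with the straddle limit stated;
- use baseline weight throughout;
- state when the 72 hours start and how missing intervals are handled;
- record catheter status.

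**Fallback.** If entries of 6 hours or less are not available, redefine endpoint 2 as sustained oliguria on the 12- and 24-hour totals.

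**Separately.** State which intake/output data the Stage II and III urine criteria are judged from, and reconcile this with the recording intervals. No clinical rule is proposed here.

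**Cost.** Fixed windows give 72/6 = 12 values per patient. The present plan gives 24/12 + 48/24 = 4, if the 24-hour totals cover hours 24 to 72. The difference is up to 140 × (12 − 4) = 1,120 extra values; rolling windows need more. This assumes the nursing records already hold such entries. Two downsides remain: without a catheter, a long gap between voids can read as false oliguria, and fixed windows still miss some straddling episodes.

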Participants will receive routine care for their acute decompensated heart failure. Currently, many practitioners utilize both intermittent and continuous furosemide infusions in this patient group. Low dose, or renal-dose dopamine is also a frequent adjunct to diuretics to aid in diuresis.

e. Justification for inclusion of a placebo or non-treatment group.

There is no placebo group.

f. Definition of treatment failure or participant removal criteria.

Subjects will be removed from the protocol for:

1. The development of hemodynamic instability including hypotension (SBP < 90), hypertensive emergency, or unstable arrhythmias (SVT or VT).
2. The development of pulmonary edema requiring inotropes or vasopressor or more than 50% inspired oxygen.
3. The development of acute coronary syndrome.
4. The development of acute kidney injury by KDIGO criteria as follows¹:
 - a. If the patient develops Stage II AKI (by KDIGO criteria), the study treatment will be held and a clinical decision will be made whether to resume or discontinue treatment drug
 - b. If the patient develops Stage III AKI (by KDIGO criteria), the study treatment will be discontinued and the patient will be classified as treatment failure and followed only for outcome recording.
5. The need for renal replacement therapy
6. New atrial fibrillation or other supraventricular tachyarrhythmia
7. Sustained ventricular arrhythmias

8. Requirement of furosemide dose increase beyond the study maximum of 200 IV twice daily (or 400 IV over 24 hrs), or the need for addition of thiazide diuretic.

g. Description of what happens to participants receiving therapy when study ends or if a participant's participation in the study ends prematurely.

Once the study period ends, or if the study ends prematurely, the patient will receive standard heart failure management at the discretion of the primary team. The patient will resume standard outpatient follow up as advised by the primary team at the time of discharge.

5. Inclusion/Exclusion Criteria

a. Inclusion Criteria :

1. Admission to the hospital for acute decompensated heart failure within 24 hours of enrollment into the study.
 - a. Diagnosis of heart failure as defined by the presence of at least 1 symptom (dyspnea, orthopnea, or edema) AND 1 sign (rales on auscultation, elevated jugular venous pulse, hepatojugular reflex, peripheral edema, ascites, pulmonary vascular congestion on chest radiography)
2. Patient ≥ 18 years of age

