3. Estimated GFR of $> 15 \text{ mL/min/1.73m}^2$ determined by the Chronic Kidney Disease Epidemiology Collaboration (CKD- EPI) equation
4. Willingness to provide informed consent
5. Known ejection fraction by noninvasive testing of $\geq 50\%$ within 12 months of admission to the hospital with no interval myocardial infarction since inclusion TTE, by history, or by ECG.
6. Negative pregnancy test in a female of child bearing potential
7. Willingness of primary attending physician for patient to participate.

b. Exclusion:

1. Systolic BP < 90 mmHg on admission
2. Hemoglobin (Hgb) < 8 g/dl
3. Known allergy or intolerance to furosemide or low dose dopamine.
4. Hemodynamically significant arrhythmias including supraventricular tachycardias not responsive to rate control therapies or resulting in hemodynamic instability, ventricular tachycardia, or defibrillator shock within 4 weeks
5. Acute coronary syndrome within 4 weeks as defined by electrocardiographic (ECG) ST-segment depression or prominent T-wave inversion and/or positive biomarkers of necrosis (e.g., troponin) in the absence of ST-segment elevation and in an appropriate clinical setting (chest discomfort or anginal equivalent)
6. Cardiac diagnoses in addition to or other than HFPEF:
 - i. Active myocarditis
 - ii. Hypertrophic obstructive cardiomyopathy
 - iii. Severe valvular disease

- iv. Restrictive or constrictive cardiomyopathy, including known amyloidosis, sarcoidosis, hemochromatosis
 - v. Complex congenital heart disease
 - vi. Constrictive pericarditis
 - vii. Severe pulmonary hypertension (RVSP \geq 60), not secondary to HFPEF
- 7. Non-cardiac pulmonary edema
 - 8. Clinical evidence of digoxin toxicity
 - 9. Received IV vasoactive treatment or ultra-filtration therapy for heart failure since initial presentation
 - 10. Anticipated need for IV vasoactive treatment or ultra-filtration for heart failure during this hospitalization
 - 11. History of temporary or permanent renal replacement therapy or ultrafiltration within 6 months
 - 12. History of renal artery stenosis > 50%
 - 13. Need for mechanical hemodynamic support
 - 14. Sepsis
 - 15. Terminal illness (other than HF) with expected survival of less than 1 year
 - 16. Previous adverse reaction to the study drugs
 - 17. Enrollment or planned enrollment in another randomized clinical trial during this hospitalization
 - 18. Inability to comply with planned study procedures
 - 19. Pregnancy or nursing mothers

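### Exclusion 5 defines recent acute coronary syndrome without ST-elevation infarction, and inclusion 5 closes that gap only when the infarct came after the qualifying echocardiogram

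*Combined protocol and SAP*

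**What the plan says.** All of the text is in the combined protocol and SAP.

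- **Section 5.b, exclusion 5.** The criterion opens with the general term and a definition: "Acute coronary syndrome within 4 weeks as defined by electrocardiographic (ECG) ST-segment depression or prominent T-wave inversion and/or positive biomarkers of necrosis". The last limb of that definition, with its qualifier, reads: "positive biomarkers of necrosis (e.g., troponin) in the absence of ST-segment elevation and in an appropriate clinical setting".
- **Section 5.a, inclusion 5.** The ejection fraction must be known from noninvasive testing and be at least 50%. The timing condition is "within 12 months of admission to the hospital with no interval myocardial infarction since inclusion TTE", and the infarct may be identified by history or by ECG. It carries no ST-segment qualifier.
- **Section 4.a, baseline assessments.** The list includes "Transthoracic echocardiogram if one has not been obtained within 1 year prior to admission". Baseline ECG and high-sensitivity troponin are on the same list.
- **Section 4.f, removal criterion 3, repeated under the early stopping rules in section 7.** The wording is "The development of acute coronary syndrome", with no definition and no ST-segment qualifier.
- **Section 4.a, treatment groups.** Allocation is 1:1:1:1 to four groups, two of which include dopamine.

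**The concern.** The head term of exclusion 5 is broader than its definition. A screener who applies the definition as written asks whether there was ST depression, prominent T-wave inversion or a positive necrosis biomarker, without ST elevation. An ST-elevation MI in the same 4 weeks does not fit. The protocol gives no reason for treating the two forms differently.

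What is at stake is participant safety and consistent screening. Section 8.a lists chest pain and fast or irregular heart rates among the common effects of low-dose dopamine, and ventricular arrhythmia among the serious but uncommon ones. Section 8.b says that the exclusion criteria are meant to limit enrolment of patients prone to side effects. An exclusion that omits one form of the condition it names serves that aim less well than it appears to. Two sites or two screeners could also reach different decisions on the same patient.

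**Working it through.** No sample size, error rate or effect estimate enters this point, so there is no figure in the plan to reproduce. The check is to apply the criteria to each kind of patient.

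**Step 1: does another criterion name ST-elevation MI?**
- Exclusions 1, 4, 9, 10 and 13 concern blood pressure, arrhythmia, vasoactive or ultrafiltration treatment, and mechanical support.
- Exclusion 6 lists other cardiac diagnoses, but not infarction.
- The description of hemodynamic instability in section 8.b does not mention infarction.
- The removal criterion concerns events that develop on study, not history at entry.

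Only inclusion 5 remains.

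**Step 2: apply exclusion 5 and inclusion 5 together, on the literal reading of exclusion 5.** Assume an event within 4 weeks, a qualifying TTE with ejection fraction of at least 50%, and no other criterion failed.

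| Case | Exclusion 5 | Inclusion 5 | Result |
|---|---|---|---|
| (a) ST-elevation MI after the qualifying TTE | Not met | Fails: MI since the TTE | Ineligible |
| (b) ST-elevation MI before the qualifying TTE | Not met | Passes: no interval MI | Eligible |
| (c) Non-ST-elevation ACS meeting the definition, any TTE date | Met | Not needed | Ineligible |

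The gap is case (b).

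**Step 3: can case (b) arise under the protocol?** Yes. Inclusion 5 accepts an echocardiogram from the 12 months before admission, so one done after an infarct three weeks ago qualifies. If there was none in the prior year, the baseline list calls for one at this admission, which again comes after the infarct.

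**Step 4: does the other reading of the qualifier remove the gap?** The phrase about ST elevation could attach only to the biomarker limb after the and/or.
- An ST-elevation MI whose ECG also showed ST depression or prominent T-wave inversion would then meet the first limb and be excluded.
- An ST-elevation MI without those changes would still meet neither limb.

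The gap becomes narrower but stays open, and the text does not say which reading applies.

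**Step 5: exposure.** With equal allocation to four groups, the expected share of case (b) patients given dopamine is 2/4 = 50%. The number of such patients cannot be derived from the documents.

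**The case against.** The strongest reply is that this is loose drafting with little reach. Inclusion 5 already bars an infarct of any type since the qualifying TTE. The head term of exclusion 5 is general, and the removal criterion uses ACS without a qualifier, so a reasonable investigator would probably take the exclusion to mean all ACS. The attending physician must also agree to participation (inclusion 7). Baseline ECG and troponin, telemetry and a heart-rate rule for the dopamine infusion give some protection.

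Much of this stands, and it limits the point. A reader might infer from exclusion 5 alone that any ST-elevation MI in the past 4 weeks is eligible. The documents do not support that, because case (a) fails inclusion 5. Nor does the text exclude all unstable angina: the definition needs ECG changes or biomarkers. A reader might also say that the rule works against its own purpose by admitting the more severe event. The protocol states no purpose specific to exclusion 5 and does not rank the two forms, so that argument goes beyond the text.

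The reply does not close case (b). Investigator discretion is not a criterion, and the monitoring measures act after enrolment or do not address a past infarct.

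**Conclusion.** The point holds in a narrow form. As worded, exclusion 5 does not cover an ST-elevation MI within 4 weeks, and inclusion 5 leaves uncovered those that came before a qualifying TTE with an ejection fraction of at least 50%. On the alternative reading of the qualifier, the uncovered group is smaller and screening may be inconsistent.

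The size is unknown. That the number is probably small is a judgement: it needs a recent infarct, a later echocardiogram with preserved ejection fraction, an admission for decompensated heart failure, and no other criterion failed. Nothing here shows an effect on the primary endpoint, the error rate or the analysis.

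A reader might infer that the removal criterion shares the gap. It does not on its face, because it is unqualified. The difficulty is only that exclusion 5 holds the document's sole definition of ACS. If that definition is carried over, the removal wording narrows; if it is not, the same term has two meanings.

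This is worth correcting for safety and consistency, but it is not a defect on which the trial stands or falls.

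**What to change.** Reword exclusion 5 so that its definition matches its head term and covers ACS in the previous 4 weeks with or without ST-segment elevation. If the omission of ST-elevation MI is intended, say so explicitly and give the reason. Either way, place the qualifier so that it is clear which limb it governs.

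Then reconcile exclusion 5 with inclusion 5 and with the ACS removal criterion in section 4.f and the early stopping rules, so that a reader knows whether the term means the same thing in each place. No change to the removal rule is proposed here; its content is for the sponsor and investigators.

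The cost is a short wording amendment. ECG and troponin are already baseline items, so no test is added. Broadening the exclusion would lose a few candidates at most.
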